There have been three reported cases of significant adverse reactions related to intranasal OT, all linked to OT's potential to exert antidiuretic effects in high doses (by binding vasopressin receptors in the kidney; Joo et al., 2004). The first two of these reports involved the excessive use of intranasal OT and excessive IV hydration (Mayer-Hubner, 1996; Seifer et al., 1985), and the third was the result of long-term intranasal OT use (2.8-5.6 IU thrice-daily for 4 weeks; Anseau et al., 1987). All three cases noted a decrease in the patients' plasma sodium and osmolality levels. OT has a very small -- 0.25 % -- affinity for the renal AVP system (Liggins, 1963). Therefore, it can theoretically cause a syndrome similar to inappropriate ADH/AVP secretion -- SIADH, although carefully controlled human studies without water intoxication have not substantiated a natriuretic or antidiuretic effect in humans (Rasmussen et al., 2004). In none of [name] studies were changes in sodium levels or osmolality noted, including those administering up to 168 IU of intranasal OT for 6 weeks. Additionally, cardiovascular effects have not been noted in intranasal human trials with non-pregnant patients, including longer-term trials of higher dose (den Boer & Westenberg, 1992; Epperson et al., 1996).

The dose given in our research will be lower than in most other studies. For example, Epperson and colleagues (1996) gave five participants with OCD 160 IU of intranasal OT daily for a week and another two patients 320 IU/day for a week and found no adverse effects with either dose including measures of blood pressure and osmolality. [name] team has substantial experience with participants in a number of different studies receiving intranasal OT in various doses up to 168 IU (84 IU twice a day). They have administered 80 IU / day (40 IU twice a day) to patients with GAD for 3 weeks and found it was very well tolerated. In another small study looking at the effects of OT in individuals with schizophrenia, ten participants received 84 IU twice a day for 3 weeks. In another study eight schizophrenia participants received 6-weeks of 84 IU twice a day intranasal OT, while approximately 24 participants so far have received 48 IU twice a day for 12 weeks. In none of these participants was there any evidence of either subjective side effects or objective evidence of physiological adverse effects (including blood work and measurement of urine osmolality).

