In the event of severe side effects while taking either OT or the P, the blind for that participant will be broken. In this case, we will have the participant contact his or her primary care physician.

Excluded Medical Conditions. As a precaution, we will exclude participants who take vasoconstrictors such as vasopressin (e.g., desmopressin) or pseudoephedrine at time of study enrollment. Also, since OT can potentially produce antidiuretic effects (via activating vasopressin receptors on the kidney) we will exclude patients taking antidiuretic medication. As hypersensitivity to OT is a contraindication (other than certain cases of abnormal labor), we will exclude participants with a hypersensitivity to OT or vasopressin, given OT's structural similarity to vasopressin.

Drug-Interactions. Severe hypertension has been reported when OT is administered via IV during labor for 3-4 hours following prophylactic administration of a vasoconstrictor in conjunction with caudal block anesthesia. Cyclopropane anesthesia may modify OT's cardiovascular effects, producing unexpected results such as hypotension. There have not been any reports of drug-interactions with chronic intranasal OT administration in the many published studies in which patients took concomitant medications (Feifel et al., 2010; MacDonald et al., 2011; Pedersen et al., 2011).

Laboratory tests. Participants will have blood drawn at screening and during the post-intervention visit to measure their blood chemistry and will provide urine samples for osmolality tests. Abnormal results will be brought to the principal investigator's attention immediately. The results will be reviewed and

Protocol: IRB201801467 (UCOPE Study)

IRB version: 10/1/2018

PI version: 05/10/2024

signed by the study clinician and Drs. [name] or [name]. If a participant has both low sodium (<134mEq/L) and high osmolality (>1200L), we will conduct a second blood test. If the sodium is again low (<134mEq/L) in the repeat blood draw, the participant will be excluded.

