Adverse events will be defined as any physical symptoms or side effects that began following administration of the study drug. All reported and observed adverse events will be tracked in a running adverse events participant log, which will contain information regarding dates, description, and severity. All adverse events will be coded using the most current version of the Medical Dictionary for Regulatory Activities (MedDRA). The number and percentage of participants reporting treatment-emergent adverse events will be tabulated by treatment, system organ class and MedDRA-preferred term. Treatment-emergent adverse events will be those adverse events that begin or worsened following the first dose of study drug. Adverse events will be further classified by severity and investigator-assigned relationship to study drug. All reported and observed adverse events will be tracked on a running adverse events log (specific to each subject and maintained in his/her study file) and will contain information regarding onset/offset dates, time course (i.e., single, sporadic), severity, action taken regarding study drug, relationship to study drug, and whether it meets FDA criteria for "Serious." Each reported event is reviewed by the principal investigator and the study physician in a timely fashion. Additionally, the principal investigator reviews all adverse events recorded in each participant's log at the conclusion of study participation.

In Case of Emergency. Participants will have 24-hour access to emergency care and will be provided with a means of contacting the on-call study doctor and research staff. Participants will be informed and encouraged to contact the study physician and study staff immediately with medical concerns or unusual reactions. Participants will also be informed of the closest Emergency Department location to their residence.

Data and Safety Monitoring Plan. A Data Safety Monitoring Plan will be in place. In particular, the following procedures will be implemented to ensure data and participant safety. Study progress and safety will be reviewed by the principal investigators in collaboration with [name], M.D., the study MD, and [name], M.D., Ph.D., the sponsor of the IND and consultant on the project.

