intervention will be used for analysis. All participants who went through the intervention phase of the study will be followed up by phone calls at multiple time points to ensure safety; every 7 days during the intervention, 7 days post intervention, 3 months post intervention, and 6 months post intervention. Progress reports, including participant recruitment, retention/attrition, and adverse events will be provided to an Independent Safety Monitor(s) for reviews on a bi-annual basis. The Independent Safety Monitor(s) for this study will consist of an established senior investigator not associated with our study. A study end report will be compiled and will include a list and summary of adverse events. In addition, this report will address: (1) whether adverse event rates are consistent with pre-study assumptions; (2) reason for dropouts from the study; (3) whether all participants met entry criteria; (4) whether continuation of the study is justified on the basis that additional data are needed to accomplish the stated aims of the study; and (5) conditions whereby the study might be terminated prematurely. The annual report will be signed by the Independent Safety Monitor and will be forwarded to the IRB, NIH, and FDA. The Independent Data Safety Monitoring Plan will also require that all significant serious adverse events that may be possibly related to the study participation will be reported to the IRB, FDA, and NIH within 48 hours of the principal investigators learning of the event. In addition, any unanticipated serious adverse events that may increase the risk of the research for participants or potential participants will be reported to the IRB and the NIH within 48 hours of the principal investigators being informed about the event. This study will be stopped prior to its completion if: (1) the intervention is associated with adverse effects that significantly impact the risk-benefit ratio, (2) study recruitment or retention becomes futile, (3) any new information becomes available during the trial that necessitates stopping the trial; or (4) if independent safety monitor indicates that stopping the trial is necessary due to adverse event frequency or severity.

ClinicalTrials.gov Requirements. In accordance with Public Law 110-85 and NIH guidelines, the proposed research will be registered with ClinicalTrials.gov prior to commencement of study procedures involving participants.

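### Post-treatment sodium and urine osmolality have no by-treatment summary, no clear route into the adverse-event table when symptomless, and no repeat test for a low sodium alone

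*Combined protocol and SAP*

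**What the plan says.** All references are to the UCOPE part of the combined protocol and SAP.

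- **Schedule.** Section 6 (Intervention period for Knee OA Participants) has blood and urine checked at baseline and at the end of the intervention. The check covers sodium, osmolality and other out-of-range markers, and its purpose is to confirm that nothing adverse has happened. Section 7 (Laboratory tests) says: "Participants will have blood drawn at screening and during the post-intervention visit to measure their blood chemistry", with urine for osmolality. Phase Two is to repeat Phase One, so by inference each participant has a before-and-after pair under each treatment.
- **Handling.** Abnormal results go to the principal investigator at once, and results are reviewed and signed by the study clinician. A second blood test is required when sodium is below 134 mEq/L and osmolality is above 1200 in the same participant.
- **Adverse events.** Section 7 (Assessment of Adverse Events): "Adverse events will be defined as any physical symptoms or side effects that began following administration of the study drug". On recording: "All reported and observed adverse events will be tracked in a running adverse events participant log". On output: "The number and percentage of participants reporting treatment-emergent adverse events will be tabulated by treatment, system organ class and MedDRA-preferred term".
- **Oversight.** The Data and Safety Monitoring Plan gives the monitor twice-yearly reports covering recruitment, retention and adverse events. The end report holds a list and summary of adverse events. The numeric stopping rule counts side effects reported in the weekly calls.
- **Background risk.** Section 7 (Safety of OT in Humans) describes three significant reactions: "All three cases noted a decrease in the patients' plasma sodium and osmolality levels". It then gives reassurance. In none of one research group's studies "were changes in sodium levels or osmolality noted, including those administering up to 168 IU of intranasal OT for 6 weeks". In that group's work "approximately 24 participants so far have received 48 IU twice a day for 12 weeks", also with clean blood work and urine osmolality.

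**The concern.** Water retention with falling sodium is the mechanism-based risk that the protocol itself describes for OT, and the trial draws samples to look for it. Yet every aggregate safety output that is named runs through adverse events. A symptomless low sodium enters those outputs only if someone decides that it counts as a side effect or an observed event, and no laboratory threshold guides that decision. An average fall that leaves most people within range would enter nothing.

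The repeat-test rule adds a second gap. Because it joins two conditions, a participant who comes back from four weeks of spray with a sodium of, say, 132 and an osmolality below 1200 is reviewed, but the rule does not call for a second measurement.

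What is at stake is the quality of the safety evidence. The trial should yield sodium values on OT and on placebo in the same older adults, and the plan as written does not turn them into a comparison. Pain, function and mechanism results are not touched.

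**Working it through.** **Step 1: where could a sodium or osmolality difference between treatments appear?**

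| Named output | Does it carry laboratory values by treatment? |
|---|---|
| Table 3 and the analysis text (Section 6) | No, but these cover Aims 1 and 2, so absence here proves little |
| Adverse-event table (Section 7) | Only for values recorded as adverse events; no laboratory criterion given |
| Monitor progress reports | Not named; the list is introduced as inclusive, so not necessarily complete |
| End report | List and summary of adverse events |
| Numeric stopping rule | Reported side effects only |

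No row promises a by-treatment summary of the measured values.

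**Step 2: the plan's own figure.** The power section expects 160 × (1 − 0.20) = 128 participants at follow-up, given there as 64 on OT plus 64 on placebo. This reproduces. The documents give no count of people completing both phases, so 128 pairs is an upper working value and 64 a cautious one.

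**Step 3: what individual values would show.** The documents give no sodium mean or SD. Assume normal values with mean 140 (range 139 to 141) and SD 2.5 (range 2 to 3) mEq/L, ignoring the effect of screening.

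Expected number below 134 = 128 × Φ((134 − (mean − fall)) / SD).

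- No fall: Φ(−6/2.5) = Φ(−2.4) = 0.82%, so 1.05 people.
- Fall of 1: Φ(−5/2.5) = Φ(−2.0) = 2.28%, so 2.91 people.
- Extra: 2.91 − 1.05 = 1.86 people.
- Smallest extra over the range (mean 141, SD 2): 0.17 − 0.03 = 0.14.
- Largest extra (mean 139, SD 3): 11.68 − 6.12 = 5.56.

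Comparing 0.82% with 2.28%, with 128 per treatment treated as independent: standard error = √((0.0082 × 0.9918 + 0.0228 × 0.9772)/128) = 0.0154. The difference divided by this is 0.0146/0.0154 = 0.95. Power at two-sided 5% is Φ(0.95 − 1.96), about 16%. Counts below 134 would therefore usually miss such a shift.

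**Step 4: what a paired summary would show.** Half-width of the 95% CI for the within-person OT-minus-placebo difference = t(0.975, n−1) × SD of the difference / √n. The SD is assumed to be 2, 3 or 4 mEq/L.

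| Pairs | t | SD 2 | SD 3 | SD 4 |
|---|---|---|---|---|
| 128 | 1.979 | 0.35 | 0.53 | 0.70 |
| 96 | 1.985 | 0.41 | 0.61 | 0.81 |
| 64 | 1.998 | 0.50 | 0.75 | 1.00 |

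**Step 5: how far prior experience settles it.** This trial gives 48 IU/day. The clean experience reached 168/48 = 3.5 times that dose for 6 weeks, and 96/48 = 2 times for 12 weeks. That makes a large effect unlikely. The groups were small: eight people in the 6-week study at 168 IU/day that Section 7 describes, and about 24 at 96 IU/day.

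**The case against.** The case for leaving the plan alone has real force.

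- **Laboratory change is already treated as harm.** Section 7 calls the three case reports adverse reactions and speaks of blood work and urine osmolality as evidence of adverse effects. Read with the words for side effects and for observed events, a low sodium on treatment may well be logged, coded and tabulated. This stands as a fair reading. It is not a stated rule.
- **Individual review is mandatory.** Abnormal results are escalated at once and signed off, and nothing stops the clinician repeating a lone low sodium. Staff ask about thirst and urination, and withdrawal for weakness, low energy or mental-status change prompts laboratory tests within 48 hours. This stands, and it is the main reason for the low weight.
- **An adverse-event procedure is still to be written** and may set logging rules. Its content is not in the documents.
- **The background is mostly reassuring.** Two of the three cases involved excessive use with excessive intravenous fluid, and the protocol notes that controlled studies did not confirm an antidiuretic effect.
- **The magnitude is assumed.** The range of 0.1 to 5.6 extra people is wide, and the documents do not show that a 1 mEq/L shift within range matters clinically.

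A reader might also infer more than the documents support:

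- *That low sodium values would be ignored.* The review and sign-off requirement contradicts this.
- *That the safety samples may be skipped.* The Section 6 sentence on dropping study portions is ambiguous. The portions it lists may simply be those needing an in-person visit, and elsewhere the samples are stated as planned.
- *That a participant with low sodium after dosing would be removed from the analysis.* The exclusion sentence repeats the eligibility rule. Section 6 speaks of discontinuation for dosed participants and specifies intent-to-treat for Aim 1, and no sentence says that data would be deleted.

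**Conclusion.** The point holds at minor weight. The plan measures sodium and urine osmolality around each intervention for safety. It names no by-treatment summary, leaves it unclear whether a symptomless low sodium is an adverse event, and requires a repeat test only when two abnormalities coincide. These three gaps follow from the text and do not depend on any assumed sodium distribution.

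The numbers only illustrate the consequence. Under the stated assumptions, a 1 mEq/L average fall adds about 1.9 people below 134 (range 0.1 to 5.6 of 128), while a paired summary would give a 95% CI half-width of 0.35 to 1.00 mEq/L. Nothing here shows that OT lowers sodium at this dose; the documents suggest that any effect is probably small.

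A null table would also have a limit. Samples are planned for mornings on which the spray is withheld, with the previous dose due at 5 to 6 PM, so an effect close to dosing could be missed. Marked abnormalities should be caught by existing review, and the efficacy conclusions are unaffected.

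**What to change.** 1. **Section 7, Laboratory tests.** After dosing has started, let a sodium below 134 mEq/L on its own trigger the repeat blood test. The screening rule can stay as it is.
2. **Section 7, Assessment of Adverse Events.** State that a confirmed post-treatment sodium below 134 mEq/L counts as an adverse event even without symptoms, so that it reaches the by-treatment table and the monitor reports.
3. **Same section, one descriptive table.** Show change in sodium and in urine osmolality from that phase's baseline, by treatment and period, with the number below 134 mEq/L and the number missing. Add the within-person OT-minus-placebo difference with its 95% CI. Footnote that samples follow a skipped morning dose.

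The cost is an occasional repeat draw, possibly a few more logged events, and one table from samples already planned. No new scheduled sampling is needed.

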Exclusion criteria will align with study and safety requirements related to: **1) OT application** [hypersensitivity to OT or vasopressin, history of hyponatremia, syndrome of inappropriate antidiuretic hormone secretion, or psychogenic polydipsia, on vasoconstrictors such as desmopressin, pseudoephedrine, or antidiuretic medication, or anti-inflammatory drugs, or muscle relaxants, low sodium and high osmolality levels, blurred vision caused by a medical condition, excessive smoking, excessive drinking, muscle pain as a result of systemic disease, significant nasal pathology, previous or concurrent use of narcotics delivered intranasally (e.g., cocaine), or gastroparesis. If a participant has both low sodium (<134mEq/L) and high osmolality (>1200L), we will conduct a second blood test. If the sodium is again low (<134mEq/L) in the repeat blood draw, the participant will be excluded. Given that myocardial OT receptors,⁷⁹ when bound to, inhibit cardiovascular activity,⁸⁰ individuals with heart problems (e.g., cardiomyopathy, history of myocardial infarction, arrhythmias, prolonged QT interval), and **any form of cardiac surgery** will be excluded]. Results of blood or/and urine testing may indicate that the participant should not participate in the study (e.g., certain test results could be out of normal range). If this is the case, we will give the participant a copy of your lab results, so that the participant may share them with the participant's own medical provider and seek care if appropriate.

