Saliva, Urine and blood samples. After written informed consent, participants will provide a urine sample to determine osmolality and a fasting blood sample to evaluate standard clinical parameters (Comprehensive Metabolic Panel (CMP-14) Blood Test), which will be reviewed by Co-I [name] to determine study continuation. Following established pilot study procedures, blood samples will also be used for determination of plasma neuropeptide (e.g., OT, arginine vasopressin (AVP)) concentrations and inflammatory markers (e.g., IL-6, TNF- α , C-reactive protein (CRP)); as well as genetic markers associated with OT. This session will take place in the mornings to accommodate for fasting and to control for circadian fluctuations. For women under the age of 62, pregnancy tests will be conducted at study start. Samples may be collected during any session that is most convenient for the participants as long as this is collected before randomization. Saliva samples will be collected for additional DNA testing on genetic markers associated with OT. Saliva collection has been done previously for the study of OT and other hormones in the body.

Physical examination. Height and weight will be measured and Body Mass Index (BMI) will be calculated as it is significantly related to pain symptoms in OA.⁸³ Participants will complete a thorough Pain and Medical History Questionnaire, including a review of bodily systems assessing the reported duration of OA, current and past treatments for OA, comorbid conditions, baseline adverse events reporting, and current medication use as in our previous knee OA studies.^{5,57} Information regarding hormone replacement therapy will be obtained for both sexes, and for women, information regarding menopausal status, as this may interact with baseline OT levels and OT intervention effects.⁸⁴ If there are concerns with eligibility, participants will undergo a Physical

Examination by the study rheumatologist (Co-I [name]) to: 1) confirm the diagnosis of knee OA according to ACR clinical and radiographic criteria;⁷⁸ 2) rule out any exclusion criteria; and 3) identify the most symptomatic knee. Manual examination of joint tenderness may be performed bilaterally for hands, hips, and knees. Symptomatic hip OA is common in the knee OA population⁸⁵⁻⁸⁷ and is associated with disability⁸⁷ and thus will be included as a covariate.

[figure not shown]

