During the 4-week intervention, participants will self-administer via intranasal spray 24 IUs of OT or P twice a day at home, at 8-9AM and again at 5-6PM. Participants that take any other nasal spray, will be asked to separate sprays by 20 minutes and this will be recorded in the diary. Missed doses will not be a deviation and participants are instructed to log each day whether they took the spray or not. The utilized synthetic OT is a formulation developed in [name] lab at UCSD (IND #100,860; see letter of support from [name] and IND letter). [name] has been sub-investigator on this IND for several years.^{49,105} The drug (i.e., synthetic OT) and the P (i.e., containing all of the inert ingredients except for the OT) will be compounded at UF's Investigational Drug Services (IDS). [name] has established this compounding route together with [name], chief pharmacist at UF IDS under [name] protocol and successfully and safely implemented procedures in our pilot study. Compliance will be monitored by measuring the fluid left in the spray bottle after the treatment period and using a log that participants fill in each day during the intervention. If any time during the treatment it is determined that the participant should not continue due to adverse events, the participant will be discontinued. Furthermore, at baseline and at the end of the intervention, blood and urine samples will be checked

Protocol: IRB201801467 (UCOPE Study)

IRB version: 10/1/2018

PI version: 05/10/2024

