(e.g., for osmolality levels, sodium levels, and any other blood markers out of range) to ensure that no adverse changes have occurred during the study intervention. Additionally, before and after the intervention period participant will fill out the Goal Attainment Scale (**GAS**). For the majority of the 4-week intervention periods, participants may complete daily assessments via their Samsung Gear S® or Apple smartwatch or Oura Ring. We will be able to assess pain, mood, and activities at random times throughout the day. Participants will be contacted once a week to assess side effects and asked if they have been completing their diaries. Any symptom reported as moderate or severe will be brought to the PIs' attention and will be discussed with the study MD as needed on a case by case basis. These weekly calls will also ensure regimen compliance and will assist participants in download of the Samsung Gear S® or Apple smartwatch or Oura Ring data to a secure research server. We have successfully established a similar approach in other projects within our institute, and the DSAT Core has validated pipelines for data analysis.^{92,106}

Post-Intervention Assessments for Knee OA Participants

In the last week of the intervention, participants will be scheduled to return for up to four (or 6 with the MRI) post-intervention visits, which will be identical (with minor exceptions) to the baseline visits. Importantly, at the follow-up Health Assessment we will assess changes in health status, and their global impression of change (**PGIC/MPIC**) since starting the intervention.

Wash-out Period for Knee OA Participants

Participants will undergo a four-week wash-out period in between phases one and two. The wash-out period will serve to prevent confounding variables between both drug administrations. Four weeks is a sufficient period of time for participants to return to baseline levels prior to drug administration.

Phase Two Procedures for Knee OA Participants

After the four-week wash-out period, participants will enter phase two of the study. Phase Two is completely identical to Phase One: up to 4 (or 6 with the MRI) Baseline Visits, Intervention Period, and up to 4 (or 6 with the MRI) Post-Intervention Visits. Participants will be given the other drug from the first intervention period per randomization.

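### The low-sodium rule requires a repeat test only when osmolality is also high, so low sodium alone before dosing has no set action (cheap improvement, minor)

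*Combined protocol and SAP*

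**What the plan says.** The rule has two steps, worded the same way in the exclusion criteria (section 6) and under Laboratory tests (section 7):

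- Step 1: "If a participant has both low sodium (<134mEq/L) and high osmolality (>1200L), we will conduct a second blood test".
- Step 2: "If the sodium is again low (<134mEq/L) in the repeat blood draw, the participant will be excluded".

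The rule does not name the osmolality specimen. The sampling section points to urine: "participants will provide a urine sample to determine osmolality and a fasting blood sample to evaluate standard clinical parameters".

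Several other provisions cover abnormal results without giving a number:

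- Exclusion criteria: "Results of blood or/and urine testing may indicate that the participant should not participate in the study".
- Saliva, Urine and blood samples: a co-investigator reviews the metabolic panel "to determine study continuation".
- Intervention period: "at baseline and at the end of the intervention, blood and urine samples will be checked". Sodium and osmolality are among the values named there.
- Laboratory tests: abnormal results go straight to the principal investigator, and the results are reviewed and signed, including by the study clinician.
- Phase Two Procedures, after a four-week wash-out: "Phase Two is completely identical to Phase One".
- Procedures for Control Participants: controls who choose the spray also give a urine sample for osmolality and a metabolic panel.

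The ancillary PANDA protocol repeats the two-step rule, but it describes a cross-sectional observational study.

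**The concern.** The two steps use different conditions. Step 2 treats a low repeat sodium as sufficient to exclude, whatever the osmolality. Step 1 lets a participant reach step 2 only if osmolality was also high at the first draw. Someone with sodium below 134 mEq/L and osmolality at or below 1200 never reaches the test that could exclude them.

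The plan's own account of the risk makes sodium the natural trigger. Safety of OT in Humans (section 7) cites three significant reactions to intranasal oxytocin, linked to its antidiuretic action. Plasma sodium and plasma osmolality fell in all three. The exclusion criteria also bar a history of hyponatremia with no osmolality condition.

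Everyone who completes both phases takes oxytocin in one of them. Two people with the same low sodium and unremarkable osmolality could be handled differently, one retested and excluded and the other dosed, and both decisions would comply with the rule.

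A second, smaller gap is that the rule under Laboratory tests follows a sentence covering both the screening draw and the post-intervention draw, yet its only outcome is exclusion. It does not say what that means for someone already dosed, although Aim 1 is to be analysed by intent-to-treat.

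**Working it through.** **The rule, case by case**

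1. Sodium <134, osmolality >1200: repeat required; excluded if the repeat sodium is also <134.
2. Sodium <134, osmolality ≤1200: no repeat and no exclusion prescribed; clinician review only.
3. Sodium ≥134, osmolality >1200: no numeric action.
4. Sodium ≥134, osmolality ≤1200: no action.

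Case 2 is the gap.

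**Does anything else close case 2?**

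- The history-of-hyponatremia exclusion has no threshold and concerns the past, not a new laboratory value.
- The exclusion list also names low sodium together with high osmolality. That might be read as two separate exclusions, but it gives no number, and the rule that follows requires both.
- The general reviews have no cut-off and no set action.

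Nothing closes it.

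**How many checks are involved**

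Inputs: 160 enrolled and 128 remaining after 20% attrition (Power and sample size considerations); 160 controls planned (Participants); two phases, each with a baseline and an end check (Intervention period; Phase Two Procedures).

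- Checks before dosing, treated sample: 160 at the phase one baseline plus 128 to 160 at the phase two baseline. 160 + 128 = 288; 160 + 160 = 320.
- Controls who choose the spray: 0 to 160, one check each. The total before dosing is 288 to 320 + 160 = 480.
- Adding end-of-intervention checks: 160 + 3 × 128 = 544 if all attrition falls before the first end check; 4 × 160 = 640 if nobody drops out; 640 + 160 = 800 with all controls.

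People screened but not enrolled are not counted, since their number is not given.

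**How many extra repeats**

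Extra repeats = checks × p, where p is the share of checks falling in case 2. The documents give no rate of sodium below 134 and no distribution of osmolality, so p is unknown and no estimate follows. For scale only, each 1% of checks in case 2 would mean about 3 to 5 repeats before dosing (288 × 0.01 = 2.9; 480 × 0.01 = 4.8), or about 5 to 8 over all checks (544 × 0.01 = 5.4; 800 × 0.01 = 8.0). This measures workload, not harm.

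**The case against.** The strongest reply is that a low sodium would not be missed. The panel goes to a designated co-investigator, abnormal results are escalated and signed, staff make weekly side-effect calls and ask about thirst and urination, and safety labs follow within 48 hours if someone withdraws with weakness, low energy or mental-status change. The exclusion criteria also remove SIADH, psychogenic polydipsia and antidiuretic use. This stands, and it is why the point is minor. It does not supply a set action for case 2.

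The pairing may also be deliberate, aimed at an SIADH-like picture. A reader might infer that asking for high osmolality is a mistake, because the case reports describe a fall. The documents do not support that: the reports concern plasma osmolality, whereas the sampling sections measure it in urine. No reason for the pairing is given, but nothing shows it to be an error.

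A reader might also want anyone with a low value at the end of phase one barred from phase two. The documents do not support that either. There is a four-week wash-out and then a further baseline. If oxytocin caused the fall, that person's second period is placebo, so barring it prevents no oxytocin exposure. It would also make loss of the second period depend on treatment, and the mixed model's handling of missing data relies on missing-at-random.

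**Conclusion.** The point holds as a cheap improvement of minor severity. Before dosing, sodium below 134 mEq/L with osmolality at or below 1200 has no required repeat test, although a low repeat sodium alone would exclude. What happens next rests on clinician judgement.

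It would be wrong to conclude that participants with low sodium will be dosed unnoticed, or that this regimen is expected to lower sodium. The reviews argue against the first. On the second, the protocol reports no sodium or osmolality changes in earlier studies at up to 168 IU for six weeks, against 48 IU daily for four weeks per phase here.

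The conclusion rests on two readings: that the word joining the two conditions in step 1 means what it says, and that an identical phase two includes the baseline laboratory panel. The incomplete osmolality unit may be an artefact of text extraction, and nothing here depends on it.

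**What to change.** In the exclusion criteria (section 6) and Laboratory tests (section 7):

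- Let sodium below 134 mEq/L alone trigger the repeat blood test at every check before dosing: the phase one baseline, the phase two baseline after wash-out, and the panel for controls who choose the spray.
- If the repeat is also below 134 mEq/L, withhold the spray. Osmolality is still measured and remains available to the clinician for interpretation.
- For a low value at the end of an intervention, repeat the test and let the phase two baseline recheck decide whether dosing resumes. Do not bar phase two automatically.
- State that data already collected stay in the intent-to-treat analysis.

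Leave the existing clinician reviews as they are. Leave the PANDA wording unchanged, since that study gives no oxytocin and there is no dosing risk to prevent.

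The cost is a small number of extra draws and exclusions, which the documents do not allow to be estimated, and slightly less applicability to people with mildly low sodium. Someone whose sodium is still low at the phase two baseline loses the second period. Requiring two low values limits exclusions from a single stray result.
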